#### If the stop date is partial:

1. If only the day is missing:
  - 1.1. The missing day will be imputed as the last of the month, adjusting for the leap year.
2. If both day and month are missing:
  - 2.1. If the year of the AE end date coincides with the maximum of (the year of first study drug administration date or the year of the last study drug administration), then the missing month will be imputed as the month of the corresponding study drug

administration date (first or last) and the missing day will be imputed as the last of the month adjusting for the leap year.

- 2.2. Otherwise, the missing day and month of the AE stop date will be imputed as the “31” and “12”.

#### **6.2.2. Derivation of Prior and Concomitant Medication for Missing or Incomplete Dates**

If both start and end dates of medications are completely missing, no imputation will be performed, and those medications will be considered both prior and concomitant medications.

##### If the end date is partial:

1. If only the day is missing
  - 1.1. If the year and month coincide with those of the last study drug administration date, then the end of medication will be set to the last study drug administration date.
  - 1.2. If the year and month do not coincide with those of the last study drug administration date, then the missing day will be imputed as the last day of the month considering leap year and month in consideration.
2. If both day and month are missing
  - 2.1. If the year coincides with that of the last study drug administration date, then missing month and day will be imputed as the month and day of the last study drug administration.
  - 2.2. If the year does not coincide with that of the last study drug administration date, then the missing month and day will be imputed as “12” and “31”, respectively.

##### If the start date is partial:

1. If only the day is missing
  - 1.1. If the year coincides with that of the first study drug administration date, then do the following:
  - 1.2. If the month does not coincide with that of the first study drug administration date, then impute the missing day as “01”.
  - 1.3. If the month coincides with that of the first study drug administration date
    - 1.3.1. If the end date is greater than the first study drug administration date, then impute the missing day as the day of the first study drug administration date
    - 1.3.2. If the end date is less than or equal to the first study drug administration date, then impute the missing day as the day of the end date of medication.
  - 1.4. If the year and the month do not coincide with those of the first dose date, then impute the missing day as “01”.
2. If both day and month are missing:
  - 2.1. If the year does not coincide with that of the first study drug administration date, then impute missing month as “01” and missing day as “01”.
  - 2.2. If the year coincides with that of the first study drug administration date
    - 2.2.1. If the end date is greater than the first study drug administration date, then impute the missing day and month as those of the first study drug administration.

2.2.2. If the end date is less than or equal to the first study drug administration date, then impute the missing day and month as those of the end date of the medication.

2.3. If the start date is completely missing, the missing start date will be set as the earlier of the first study drug administration date and end of the medication date.

For meningococcal vaccination, the missing end date will not be imputed.

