**Table 1: Randomization Strata**

Strata	ALS Muscle Weakness at the Onset	Background ALS Therapy (Riluzole or Edaravone) at Study Entry	
	(Bulbar vs. Not)	On Stable Riluzole	On Stable Edaravone
1	Not bulbar	No	Yes, No
2	Not bulbar	Yes	Yes
3	Not bulbar	Yes	No
4	Bulbar	No	Yes, No
5	Bulbar	Yes	Yes
6	Bulbar	Yes	No

a Stable riluzole: at least 30 days on riluzole prior to Day 1.

b Stable edaravone: at least 60 days on edaravone prior to Day 1.

Abbreviations: ALS = amyotrophic lateral sclerosis; vs = versus

Patients who do not enter the study on riluzole and/or edaravone will not be permitted to start treatment with either drug during the RCP.

[figure not shown]
One unblinded interim analysis for futility is planned when approximately 33% of originally planned patients (N = 354) complete the Week 26 visit for the RCP. An independent data monitoring committee (IDMC) will be established to conduct this unblinded interim analysis and periodic review of accumulating data for patient safety and efficacy during the study. Details of the interim analysis methods are described in a separate interim analysis plan (IAP).

**OLE Period:** For each participant, the RCP ends, and the OLE Period starts, when the participant has completed the Week 50 visit assessments and received the first dose for the OLE. Regardless of the randomized assignment, all patients will receive ravulizumab during the OLE Period. Blind to the randomized treatment assignment will be maintained for patients and providers during the OLE Period until the end of the study. Initiation of riluzole and/or edaravone is permitted during the OLE Period. The first dose of the OLE Period will be administered in a blinded fashion to accommodate the loading dose for the patients originally randomized to placebo (see protocol for further details).

The OLE Period will continue for up to 2 years or until ravulizumab is approved and/or available (per country-specific regulations), whichever occurs first.

After the End of Treatment Visit or early discontinuation, patients will be followed for an additional 8 weeks after their last dose of the study drug.

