**Table 18: Protocol Deviation Categories**

1. Eligibility and entry criteria	6. Visit schedule
2. Investigational product	7. Study procedure/tests
3. Concomitant medication	8. Randomization
4. Informed consent	9. Safety reporting
5. Laboratory assessment	10. Source document
	11. Other

The following protocol deviations will be determined programmatically:

1. Participants who did not take at least 80% of the required treatment doses in RCP
2. Participants who were incorrectly stratified

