**6.1.5. Prior and Concomitant Medications / Therapies**

Prior medications are defined as medications with a start date occurring before the first study dose of the RCP. Concomitant medications (RCP) are defined as medications taken during RCP, i.e., either with a stop date after the first study dose of RCP or ongoing during RCP. Concomitant medications (OLE) are defined as medications taken during OLE, i.e., either with a stop date after the first study dose of OLE or ongoing during OLE.

Medications will be coded using the WHODrug Dictionary version in use at the time of the analysis. The number (%) of participants using prior and concomitant medications will be summarized based on the WHO Anatomical Therapeutic Chemical Level 3 Class code and

generic name for FAS. All meningococcal vaccinations and prophylactic antibiotic medications after receiving meningococcal vaccine for subjects who initiated study drug will be listed separately as well.

Nonpharmacologic therapies and procedures will be reported by treatment group and overall for the SS using SOC and PT.

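### SAP 6.2.2 gives a Day 1 start to a medication with a same-year year-only or wholly missing start and a later known end, so the record is lost from the prior-medication table

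*SAP*

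**What the plan says.** SAP 6.1.5 sets the test: "Prior medications are defined as medications with a start date occurring before the first study dose of the RCP". Protocol 9.4.4 defines prior medication in the same sense.

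SAP 6.2.2 then says how incomplete dates are handled:

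- Both dates completely missing: nothing is imputed and "those medications will be considered both prior and concomitant medications".
- Year-only start in a year other than that of Day 1 (rule 2.1): 1 January of the recorded year.
- Year-only start in the Day 1 year, end after Day 1 (rule 2.2.1): "then impute the missing day and month as those of the first study drug administration".
- Year-only start in the Day 1 year, end on or before Day 1 (rule 2.2.2): "then impute the missing day and month as those of the end date of the medication".
- Start wholly missing (rule 2.3): "the missing start date will be set as the earlier of the first study drug administration date and end of the medication date".

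The section makes no exception for ALS therapy. Protocol inclusion criterion 7 and Protocol 6.5.1.2 require at least 30 days of riluzole, or 60 days of edaravone, before Day 1 in patients who enter on these drugs. Protocol 6.5.1.2 also bars patients who enter on neither from starting one in the Randomized Controlled Period (RCP). SAP Table 1 carries the same limits into the strata, for example "Stable riluzole: at least 30 days on riluzole prior to Day 1".

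**The concern.** Prior status needs a start strictly before the first dose. A start set equal to the first-dose date fails that test by construction, whatever the true date. For a drug that the patient had to be taking weeks before Day 1, the rule replaces an unknown date with one that the eligibility criteria rule out.

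The section is also inconsistent with itself. A drug with no dates at all is prior and concomitant. Add one fact, a known end after Day 1, and the prior status disappears. A later end is no evidence against an earlier start.

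What is certainly at stake is the prior-medication table. Other outputs also depend on background therapy: time since first use of riluzole and edaravone (SAP Table 17), the planned-versus-actual strata tabulations (SAP 5.2), the programmed deviation for "Participants who were incorrectly stratified" (SAP 6.1.3) and the liver-laboratory subgroups by stable use (SAP 5.7.5.2). They are affected only if they reuse the imputed dates.

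**Working it through.** The plan states no figure to reproduce here, so the check applies the rules to dated examples.

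**Inputs.** Day 1 = 15 Sep 2020 (assumed). The start-date rules are from SAP 6.2.2, the test for prior (start before Day 1) from SAP 6.1.5, the 30- and 60-day limits from SAP Table 1, and months = 12 × (Day 1 − first use) / 365.25 from SAP Table 17.

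**Step 1: classification.**

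| Recorded start | Recorded end | Rule | Start used | Days before Day 1 | Prior? |
|---|---|---|---|---|---|
| 2020 | 1 Mar 2021 | 2.2.1 | 15 Sep 2020 | 0 | No |
| missing | 1 Mar 2021 | 2.3 | 15 Sep 2020 | 0 | No |
| 2019 | 1 Mar 2021 | 2.1 | 1 Jan 2019 | 623 | Yes |
| Feb 2020 | 1 Mar 2021 | 1.2 | 1 Feb 2020 | 227 | Yes |
| 2020 | 1 Aug 2020 | 2.2.2 | 1 Aug 2020 | 45 | Yes |
| missing | 1 Aug 2020 | 2.3 | 1 Aug 2020 | 45 | Yes |
| missing | missing | opening line | none | – | Yes, and concomitant |
| 2020 | none (ongoing) | 2.2.1 and 2.2.2 both need an end date | no answer | – | Undefined |

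Only the first two rows lose prior status wrongly for a drug in use at entry. Rows 2 and 7 differ only in whether the end date is known, and they get opposite answers.

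Rule 1.3.1 also yields Day 1, when only the day is missing, the month is that of Day 1 and the end is later. It hardly touches background therapy, because a start at least 30 days before Day 1 almost always falls in an earlier month.

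**Step 2: time on drug, if Table 17 reuses the imputed date.** Row 1 gives 12 × 0 / 365.25 = 0 months. A true start of 10 Feb 2020 would give 12 × 218 / 365.25 = 7.2 months. The earliest date consistent with the recorded year, 1 Jan 2020, gives 12 × 258 / 365.25 = 8.5 months.

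For an eligible patient with a year-only start, the understatement is at least 12 × 30 / 365.25 = 0.99 month for riluzole and 12 × 60 / 365.25 = 1.97 months for edaravone. It is at most 12 × 365 / 365.25 = 11.99 months. A wholly missing start has no such upper limit from the recorded date.

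**Step 3: stratum, if stable use is derived from the imputed date.** Zero days fails both the 30- and the 60-day limits. Under SAP Table 1:

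- Riluzole only: stratum 3 becomes 1, or 6 becomes 4.
- Both drugs, riluzole start affected: 2 becomes 1, or 5 becomes 4.
- Both drugs, edaravone start affected: 2 becomes 3, or 5 becomes 6.
- Edaravone only: stays in 1 or 4, because those strata pool edaravone yes and no.

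**Step 4: is the date reused?** SAP 6.2.2 is headed for prior and concomitant classification only. SAP Table 17, SAP 5.2 and SAP 6.1.3 do not refer to it, and they name no other rule for missing dates and no source for stable use. Steps 2 and 3 are therefore conditional; Step 1 is not.

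**The case against.** The best defence is that the branch is narrow. Year-only starts in earlier years go to 1 January and stay prior, and records with both dates missing stay prior. Inclusion criterion 7 admits treated patients only if they have no plan to stop or change dose, so most background-therapy records should be ongoing. An ongoing record has no end date and does not clearly reach rule 2.2.1. Protocol 8.3.7.2 asks for start and end dates of concomitant medication, and Protocol 8.3.7.1 asks for every ALS therapy ever used before the first dose. An affected drug still appears in the concomitant table.

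Most of this stands, and it limits the reach of the point. It does not rescue the rule: where the branch applies, the result is wrong, and nothing elsewhere corrects it. The ongoing case is a further gap. For an ongoing drug with a same-year year-only start the section gives no answer, and it does not say whether an ongoing drug counts as having a missing end date.

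A reader might infer that every missing or year-only start moves to Day 1. Rule 2.1 and the opening line show otherwise. A reader might also infer that patients will be reported in the wrong stratum. The SAP does not say that stable use comes from medication dates, and edaravone-only users could not move in any case. Nor can a patient count be derived: the documents give neither the rate of partial dates nor the number of users with a recorded stop after Day 1, which is the relevant base.

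**Conclusion.** The point holds in a limited form. For a year-only start in the Day 1 year, or a wholly missing start, with a known end after Day 1, SAP 6.2.2 produces a record that fails the SAP's own test for prior medication and conflicts with its own opening line. For riluzole or edaravone in use at entry by a patient who met the eligibility criteria, the imputed start is untrue.

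The certain consequence is misclassification in the prior-medication table. Zero months since first use, a changed derived stratum or a false mis-stratification flag would follow only if imputed dates are reused, and the SAP leaves that open.

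The number of affected records is not given and is likely to be small. No efficacy conclusion changes: SAP 5.1 makes all p-values and confidence intervals descriptive after futility, and the liver subgroups carry no p-values. The correction is still worth making, because descriptive tables are most of what this SAP now delivers.

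**What to change.** Change SAP 6.2.2 in three places.

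1. If the recorded part of the start date does not exclude a start before the first dose, and the medication ended after the first dose or is ongoing, class it as both prior and concomitant. This extends the opening line, closes the gap for ongoing drugs and also covers rule 1.3.1.
2. State that dates imputed under 6.2.2 are not used for time since first use, stable use or derived strata. Leave time since first use missing when the start cannot be placed.
3. Name the source of stable use: the riluzole and edaravone use recorded at screening. Both Protocol Table 7 and SAP Table 17 refer to use at screening; that the case report form holds it drug by drug is an assumption. The yes/no answer to inclusion criterion 7 will not serve. The criterion constrains only patients already on therapy and its note admits untreated patients, so meeting it does not show which drug, if any, a patient takes.

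The cost is a few sentences and a small programming change. A few drugs that truly started after Day 1 will also appear in the prior table, and a few duration values will be missing.

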### 6.2.3. Combined Assessment of Function and Survival Scoring Example

Table 19 provides an example of the CAFS scoring technique and associated ranking. For each of the 9 participants (3 in the placebo arm and 6 in the ravulizumab arm), the ALSFRS-R change from Baseline, the death or study withdrawal information is provided. Each participant is followed for a maximum of 12 months. Participants PPD died at Months PPD and PPD respectively, with the last available ALSFRS-R change scores being -12 and -7. Participant PPD dropped out at Month 1, with the last ALSFRS-R change score being 3 (showing improvement). For the rest of the participants that completed 12 months of follow-up, the last ALSFRS-R change from Baseline scores are shown in the fifth column. The ALSFRS-R slopes are calculated based on the ratio of change from Baseline score and the time on study; for example, for Participant PPD the slope is calculated as  $-17/12 = -1.41$ . Columns c1 to c9 provide the points (-1, 0, 1) based on the pairwise comparison for each participant with the rest of the 8 participants. Columns c2 and c9 are shaded for ease of identification, as both these participants died. Note, a point of 0 is assigned to each participant against himself by default.

Let us first consider the nondeaths for which the points will be awarded solely based on the ALSFRS-R slopes. Participant PPD slope = 0.0) gets a positive point (+1) when PPD slope is compared with the slopes for Participants PPD as each of those participants has declined at a higher rate (corresponding slopes being -1.41, -0.33, -0.25 and -1.0, respectively). When compared with Participants PPD Participant PPD receives a negative point (-1), as those participants declined at a lower rate (in fact, improved) with corresponding slopes being 0.16 and 3.0, respectively). Lastly, when compared with the 2 participants who died, Participant PPD automatically receives a positive point (+1) because of PPD survival until the end of the study. By summing all of these points, the total CAFS score for Participant PPD becomes 4. Participant PPD receives a positive point (+1) when compared with the rest of the participants because of PPD highest positive change (least decline) and survival; the CAFS score for Participant PPD becomes 8. The scores for the remaining nondeath participants can be derived similarly, as shown in the 16th column.

Let us now consider the participants who died. For example, Participant PPD gets a negative point (-1) for all pairwise comparisons; the negative point is awarded as all participants (except Participant PPD survived. When compared with Participant PPD a negative point (-1) is awarded to Participant PPD because Participant PPD survived longer than Participant PPD. Hence, the CAFS score for Participant PPD becomes -8.

The CAFS scores are ranked irrespective of the treatment groups, with the lowest score receiving Rank 1 and the highest score receiving Rank 9.

**Table 19: Example of CAFS Scoring and Ranking**

Treatment	Participant	Time-to-death (months)	Time on study (months)	ALSFRS-R		Pairwise scores for CAFS calculation									CAFS	
				Change from baseline	Slope	c1	c2	c3	c4	c5	c6	c7	c8	c9	Score	Rank
Placebo	PPD	.	12	0	0.0	0	1	1	-1	-1	1	1	1	1	4	7
		PPD	.	-12	.	-1	0	-1	-1	-1	-1	-1	-1	-1	-1	-8
Ravulizumab	PPD	.	12	-17	-1.41	-1	1	0	-1	-1	-1	-1	-1	1	-4	3
		.	12	2	0.16	1	1	1	0	-1	1	1	1	1	6	8
		.	1	3	3.0	1	1	1	1	0	1	1	1	1	8	9
		.	12	-4	-0.33	-1	1	1	-1	-1	0	-1	1	1	0	5
		.	12	-3	-0.25	-1	1	1	-1	-1	1	0	1	1	2	6
		.	12	-12	-1.0	-1	1	1	-1	-1	-1	-1	-1	0	1	-2
	PPD	.	.	-7	.	-1	1	-1	-1	-1	-1	-1	-1	0	-6	2

#### 6.2.4. Short-Form Health Survey

The 8 different dimensions of SF-36, PCS and MCS, will be calculated based on the software developed by Optum.

#### 6.2.5. Amyotrophic Lateral Sclerosis Assessment Questionnaire

The 5 ALSAQ-40 subscores will be derived per [Table 20](#).

**Table 20: Algorithms for ALSAQ-40 Subscore Calculation**

Domain	Formula
Physical mobility	$100 \times \frac{\text{Sum}(\text{Item 1 to Item 10})}{40}$
Activities of daily living/independence	$100 \times \frac{\text{Sum}(\text{Item 11 to Item 20})}{40}$
Eating and drinking	$100 \times \frac{\text{Sum}(\text{Item 21 to Item 23})}{12}$
Communication	$100 \times \frac{\text{Sum}(\text{Item 24 to Item 30})}{28}$
Emotional functioning	$100 \times \frac{\text{Sum}(\text{Item 31 to Item 40})}{40}$

#### 6.2.6. Handheld Dynamometry

The HHD megascoring will be derived as follows for Baseline and post-Baseline visits:

- For each muscle, calculate the ratio over baseline as  $100 \times (\text{visit raw value}/\text{Baseline raw value})$
- Three megascoring (ie, upper, lower, and total) are defined as the average of the nonmissing ratios for the muscles involved (upper limb, lower limb, total).
- Megascoring is always 100 at Baseline when HHD assessment is available.

If both Baseline and post-Baseline raw values are 0, then the ratio will be defined as 100. If the Baseline raw value is 0, but the post-Baseline value > 0, then the ratio will be set to missing.

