#### 4. OBJECTIVES AND ENDPOINTS

Objective	Endpoints
Primary	
To evaluate the effect of ravulizumab compared with placebo on amyotrophic lateral sclerosis functional rating scale-revised (ALSFRS-R) score in adult patients with amyotrophic lateral sclerosis (ALS)	Change from baseline in ALSFRS-R total score at Week 50
Secondary	
To evaluate the effect of ravulizumab compared with placebo on ventilation assistance-free survival (VAFS) in adult patients with ALS	Time to the earliest occurrence of 1 of the following events during the 50-week Randomized Controlled Period: 
 
• All-cause mortality
 
• First use of non-invasive ventilation (NIV) for <math>\geq 22</math> hours per day for <math>\geq 10</math> consecutive days
 
• First use of permanent assisted ventilation (PAV) for <math>\geq 22</math> hours per day for <math>\geq 7</math> consecutive days
 

To evaluate the effect of ravulizumab compared with placebo on respiratory function in adult patients with ALS	Change from baseline in percent (%) predicted slow vital capacity (SVC) at Week 50
To evaluate the safety of ravulizumab compared with placebo in adult patients with ALS	Incidence of treatment-emergent adverse events (TEAEs), treatment-emergent serious adverse events (TESAEs), and TEAEs leading to study drug discontinuation
To evaluate the effect of ravulizumab compared with placebo on muscle strength in adult patients with ALS	Percent change in combined muscle megascore from baseline at Week 50 as assessed by handheld dynamometry (HHD)
To evaluate the effect of ravulizumab compared with placebo on neurofilament light chain (NfL) concentration in adult patients with ALS	NfL concentration in serum at Week 50
To characterize the pharmacokinetics (PK) of ravulizumab in adult patients with ALS	Change in serum ravulizumab concentration over the study duration
To characterize the pharmacodynamics (PD) of ravulizumab in adult patients with ALS	Change in serum free complement component 5 (C5) concentration over the study duration
To characterize the immunogenicity of ravulizumab in adult patients with ALS	Presence and titer of antidrug antibodies (ADAs)
Exploratory	
To evaluate the effect of ravulizumab compared with placebo on respiratory function in adult patients with ALS	Time to first instance of SVC $< 50\%$ predicted during the 50-week Randomized Controlled Period

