#### **9.4.5.2. Analyses of Secondary Efficacy Endpoint(s)**

Analysis of the secondary endpoints will be performed as follows:

- **Time to VAFS:** The treatment effect on the time to VAFS will be analyzed based on a Cox's regression model treatment as a fixed effect adjusting for age, sex, baseline ALSFRS-R total score, baseline SVC, disease duration, and the stratification factor. The components of VAFS will be analyzed separately using similar models.
- **Change in SVC:** The treatment effect on SVC will be evaluated based on a MMRM with the change from baseline in SVC percent predicted as the dependent variable and following list of independent variables as fixed effects: actual time on study (months), time and treatment interaction, age, sex, baseline ALSFRS-R total score, baseline SVC, disease duration, and the stratification factor. In addition, the patient-specific random slope will be added to the model with an unstructured variance-covariance matrix. The Kenward-Rogers method will be used to estimate the denominator degrees of freedom. No imputation for the missing data will be performed after discontinuation assuming the data are MAR. This analysis will be based on the endpoint defined as the change from baseline in SVC based on the in-clinic assessment or the at-home assessment when in-clinic assessment is not available.
- **Change in muscle strength (HHD):** For each patient, a megascore will be calculated at each visit by summing scores from all muscles. The scores will be normalized by the baseline megascore multiplied by 100 (hence the baseline score is always 100%). The change from the baseline score of 100% will be used for analysis. The treatment effect on HHD will be evaluated based on a MMRM with the change from baseline in HHD as the dependent variable and following list of independent variables as fixed effects: actual time on study (months), time and treatment interaction, age, sex, baseline HHD megascore, baseline ALSFRS-R total score, baseline SVC, disease duration, and the stratification factor. In addition, the patient-specific random slope will be added to the model with an unstructured variance-covariance matrix. The Kenward-Rogers method will be used to estimate the denominator degrees of freedom. No imputation for the missing data will be performed after discontinuation assuming the data are MAR.

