### 1.1. Objectives, Estimands and/or Endpoints

Objective	Estimand/Endpoint
Primary	
To evaluate the effect of ravulizumab compared with placebo on amyotrophic lateral sclerosis functional rating scale-revised (ALSFRS-R) score in adult patients with ALS	Estimand: Difference in mean combined assessment of function and survival (CAFS) score between ravulizumab and placebo in the eligible ALS patient population after accounting for the intercurrent event (ICE) of death into the CAFS score calculation using the composite strategy. See Section 5.3 for details.
Secondary	
To evaluate the effect of ravulizumab compared with placebo on ventilation assistance-free survival (VAFS) in adult patients with ALS	Estimand: Hazard ratio (ravulizumab versus placebo) of VAFS event in the eligible ALS patient population using treatment-policy strategy
To evaluate the effect of ravulizumab compared with placebo on respiratory function in adult patients with ALS	Estimand: Difference in mean change in slow vital capacity (SVC) percent predicted score between ravulizumab and placebo at Week 50 in the eligible ALS patient population using treatment-policy strategy
To evaluate the safety of ravulizumab compared with placebo in adult patients with ALS	Endpoint: Incidence of treatment-emergent adverse events (TEAEs), treatment-emergent serious adverse events (TESAEs), and TEAEs leading to study drug discontinuation
To evaluate the effect of ravulizumab compared with placebo on muscle strength in adult patients with ALS	Endpoint: Percent change in combined muscle megascore from Baseline at Week 50 as assessed by handheld dynamometry (HHD)
To evaluate the effect of ravulizumab compared with placebo on neurofilament light chain (NfL) concentrations in adult patients with ALS	Endpoint: NfL concentrations in serum at Week 50
To characterize the pharmacokinetics (PK) of ravulizumab in adult patients with ALS	Endpoint: Change in serum ravulizumab concentration over the study duration
To characterize the pharmacodynamics (PD) of ravulizumab in adult patients with ALS	Endpoint: Change in serum-free complement component 5 (C5) concentration over the study duration
To characterize the immunogenicity of ravulizumab in adult patients with ALS	Endpoint: Presence and titer of anti-drug antibodies (ADAs)

Objective	Estimand/Endpoint
Exploratory	

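### SAP 6.2.6 replaces the protocol's summed HHD megascore with a mean of per-muscle ratios, and its zero-baseline rules let regained force lower the score

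*SAP*

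**What the plan says.** Protocol Section 9.4.5.2 builds the score in two steps. For each patient "a megascore will be calculated at each visit by summing scores from all muscles". Then "The scores will be normalized by the baseline megascore multiplied by 100", so that every patient starts at 100%. The denominator is one summed quantity, so this is a ratio of sums.

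SAP version 2, Section 6.2.6, first computes 100 × visit value / Baseline value for each muscle. It then forms upper, lower and total megascores, each "defined as the average of the nonmissing ratios for the muscles involved". This is a mean of ratios. Two rules cover muscles with no force at Baseline:

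- For a muscle that still shows no force at the visit: "If both Baseline and post-Baseline raw values are 0, then the ratio will be defined as 100".
- For a muscle that has recovered some force by the visit: "If the Baseline raw value is 0, but the post-Baseline value > 0, then the ratio will be set to missing".

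The section also states: "Megascoring is always 100 at Baseline when HHD assessment is available".

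Both documents name the same secondary endpoint: percent change from baseline at Week 50 in the combined muscle megascore (Protocol Section 4; SAP Section 1.1). The SAP's change table in Section 6.4 has no entry for Section 6.2.6. It lists changes only against SAP version 1.0, which is not among the documents supplied.

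**The concern.** Two separate things look wrong.

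The first is the formula. A ratio of sums weights each muscle by its baseline force, whereas a mean of ratios weights all muscles equally. The two agree when every muscle declines in the same proportion; otherwise they can differ in either direction. Protocol Section 2.2.1 describes limb-onset weakness as asymmetric, so uneven loss is to be expected.

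The second is the pair of zero-baseline rules. A muscle with no force at either visit is scored as fully preserved, while one that starts at zero and recovers is removed. Read together, the rules give credit for continued absence of force and withdraw that credit on recovery.

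At stake are the by-visit HHD means, changes from Baseline, figures and 95% CIs that SAP Section 5.4.2.1 still promises. With the HHD repeated-measures model deleted (SAP Section 6.4), these summaries and the accompanying listings are all that remains for this endpoint.

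**Working it through.** **Inputs.** The formulas and rules come from Protocol Section 9.4.5.2 and SAP Section 6.2.6. The number of muscles is not stated (Protocol Section 8.2.4 says only that they are prespecified, in upper and lower limbs, on both sides), and the frequency of zero baselines is not given. All muscle values below are therefore assumptions chosen for illustration.

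**Baseline value.** The plan's own figure of 100 reproduces under both definitions. The protocol gives 100 × sum/sum = 100. The SAP gives 100 for each muscle, including 0/0 = 100, and so a mean of 100.

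**Formula, no zeros.** Take five muscles at 30 and five at 10, so the baseline sum is 5×30 + 5×10 = 200.

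| Pattern of loss | Protocol: ratio of sums | SAP: mean of ratios |
|---|---|---|
| All lose 30% | 140/200 = 70 | 70 |
| Only strong muscles lose 50% | (5×15 + 5×10)/200 = 62.5 | (5×50 + 5×100)/10 = 75 |
| Only weak muscles lose 50% | (5×30 + 5×5)/200 = 87.5 | (5×100 + 5×50)/10 = 75 |

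The SAP score does not distinguish the last two patients; the protocol score separates them by 87.5 − 62.5 = 25 points.

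**Zero rules, general form.** Let k of n muscles be zero at Baseline and let the others average m percent of Baseline. Under the SAP:

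- All k stay at 0: score = ((n−k)m + 100k)/n. The change from 100 is (n−k)/n times the working muscles' mean change.
- All k regain force: score = m.
- Effect of recovery: −(k/n)(100 − m).

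This is negative whenever m is below 100. At m = 100 there is no effect. At m = 110 with n = 10 and k = 1, the score rises from 109 to 110.

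**Zero rules, numbers.** Take k = 1 and m = 60, with the working muscles at 20 falling to 12 and a regained force of 2.

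| | Stays at 0 | Regains force |
|---|---|---|
| n = 10, SAP | (9×60 + 100)/10 = 64 | (9×60)/9 = 60 |
| n = 10, protocol | 108/180 = 60.0 | 110/180 = 61.1 |
| n = 20, SAP | (19×60 + 100)/20 = 62 | (19×60)/19 = 60 |
| n = 20, protocol | 228/380 = 60.0 | 230/380 = 60.5 |

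Recovery lowers the SAP score and raises the protocol score. Excluding the zero-baseline muscle throughout gives 60 in all four situations. In a limb-group score n is smaller and the effect larger: with an assumed five muscles, (4×60 + 100)/5 = 68 against 60.

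**Group mean.** Suppose a proportion p of patients have k zero-baseline muscles that stay at 0, with n = 10 and a 40% loss elsewhere. Relative to excluding those muscles, the mean score is raised by p × (k/n) × 40.

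| p | k = 1 | k = 2 |
|---|---|---|
| 5% | 0.2 | 0.4 |
| 10% | 0.4 | 0.8 |
| 25% | 1.0 | 2.0 |

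**The case against.** **The protocol never says that a muscle's score is raw force.** If each score were already percent of baseline, summing over n muscles and dividing by the baseline sum of n × 100 would give exactly the SAP's mean of ratios. The wording does not exclude this. But the protocol mentions no per-muscle ratio, Section 8.2.4 speaks of recorded forces, and scores already expressed relative to baseline would then be normalized to baseline a second time. The raw sum is the natural reading.

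**SAP version 1.0 may have recorded the change.** This stands as a limit: the omission is established only for version 2.

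**Regained force lowers the score only if the other muscles average below 100% of Baseline.** This is correct, but it is the course the trial expects. The objection adds that the fall from 64 to 60 merely removes an unearned credit. That is also true, and the credit is itself the defect.

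**The 0/0 = 100 rule keeps every limb-group score at 100 at Baseline, even when all its muscles are zero.** This is so. It is the one case where excluding those muscles leaves the score missing. Whenever any muscle has a positive baseline, exclusion also gives 100. In the all-zero group the SAP score stays at 100 while any muscle remains at zero and becomes missing once all recover, which is hard to defend.

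**The effect of the zero rule on the treatment comparison is smaller than on arm means.** This also stands. Assume zeros are equally common in both arms and stay at zero, with working-muscle losses of 40% and 28%. The difference then moves toward zero by p × (k/n) × 12: 0.10 × 0.1 × 12 = 0.12 points, or 0.25 × 0.2 × 12 = 0.6 points in the most extreme case tabulated. This bounds only the zero rule, not the difference between formulas.

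**HHD no longer supports inference.** The model is deleted, all p-values and CIs are descriptive after futility (SAP Section 5.1), and the Hochberg procedure in Protocol Section 9.4.5.4 covers only VAFS and SVC. This limits the consequence but does not justify reporting a different quantity under the protocol's endpoint name.

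**Conclusion.** Both parts hold. SAP version 2 derives a different score from the one the protocol defines, without a recorded reason in that version. Its zero-baseline rules are inconsistent, so a declining patient's score can fall because a muscle recovered.

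The size in the trial is unknown. Protocol Section 3.2.1 expects early to mid-stage patients, so zero baselines may be few; the formula difference needs no zeros. In the illustrations, the formulas differ by 12.5 points in either direction under markedly uneven loss, recovery of one muscle costs 4 points with ten muscles or 2 with twenty, and group means shift by 0.2 to 2.0 points. The conclusion on the formula rests on reading the protocol's muscle scores as raw force. The affected output is the by-visit HHD summary of a named secondary endpoint; no inferential conclusion changes.

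**What to change.** Choose one of two routes and state it in SAP Section 6.2.6.

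1. **Protocol formula.** Score = 100 × (sum at visit)/(sum at baseline), taken over muscles measured at both, and missing if the baseline sum for that limb group is zero. The protocol gives no rule for unmeasured muscles, zero sums or separate upper and lower scores, so these are additions and should be labelled as such.
2. **Mean of ratios.** Record and justify the departure from the protocol, exclude muscles with a zero baseline at all visits (score missing if none remain), and report the protocol's summed score alongside.

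Either route costs one derivation and a few lines of text, with no new data. Under the summed score, stronger muscles carry more weight, as the protocol already implies, and the muscle set can still vary when a muscle is not measured at a visit. Under exclusion, force regained in a zero-baseline muscle no longer lowers the score, but it earns no credit either; the summed score reported alongside captures it.
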